All newly hired NGN participating in ProDeveloP will be invited to participate in the studies. Two groups (January 2023 and June 2023), each with 40–50 participants. One control group of NGNs participating in the prior introduction programme will be invited to participate in November 2022, with approximately 40-50 participants.

Design and Data Collection

The project has a prospective, longitudinal design. Both qualitative and quantitative methods will be used to answer the research questions. The questionnaires used in the study are based on validated instruments (Frögéli et al., 2019), which helps ensure the reliability of the data collected. The questionnaires will be distributed digitally via Survey and Report. One control group measurement is planned before intervention starts. Self-assessments via questionnaire are planned to be completed by the NGNs. Thereafter, self-assessments are conducted once a week during the first quarter for the intervention group. Follow-up measurements are then carried out once per quarter for up to one year after graduation. The individual interviews with NGNs and managers, and the focus groups with NGNs and supervisors, are planned to be conducted after the program has been completed. The qualitative interviews will be audio-recorded and transcribed. An overview is presented in Table 1.

Table 1. A detailed table of data collection and data analysis

Research question	Data collection	Data analysis
1	Self-assessment instruments	Descriptive statistics, regression analyses
2	a) Individual interviews b) Self-assessment instruments	a) Phenomenology b) Descriptive statistics, ANOVA, χ^2
3	Focus group interviews	Content or thematic analysis
4	a) Self-assessment instruments b) Individual interviews	a) Descriptive statistics, ANOVA, χ^2 b) Content analysis or phenomenography
5.	Focus group interviews and individual interviews	Content or thematic analysis

Timeline

Once the analyses and results have been completed and the journal editors have approved the publication; the results will be made public. Publications will take place continuously, but the doctoral thesis work is planned to be completed with a defence at the end of 2027.

Ethical Considerations

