All NGN entering the introduction year will receive written and oral information about the project. Participation is voluntary and can be withdrawn at any time. A consent form will be provided. Data will be handled confidentially, and a data management plan will be prepared. An application is approved by to the Swedish Ethical Review Board (Dnr.2022-05682-01).

5. Pre-specified statistical analysis plan

The plan comprehends a statistical analysis plan for self-assessment instruments.

Study design and study population

A quantitative intervention design with a non-randomised design with a two-arm structure is planned. The study's first arm (control group) is all eligible NGNs who participates in the previous introduction programme in September 2022. The survey for this group will be administered in late November 2022. The second arm (intervention group) comprise all eligible NGNs participating in the ProDeveloP starting either in February or in September 2023, depending on their graduation date. The surveys for group comparison will be distributed digitally in early May or December, aligned with the same time frame as the control group. Longitudinal surveys will also be collected during the intervention group's first year in ProDeveloP however this is not possible for the control group.

Inclusion criteria were newly employed NGNs who participated either in the previous introduction programme in 2022 or in ProDeveloP in 2023. Specifically, all eligible NGNs employed in 2022 who participated in the September introduction programme were included in the control group. All eligible NGNs employed in 2023 who participated in ProDeveloP,

starting in either February or September, were included to the intervention group. No explicit exclusion criteria were applied.

Outcome measures

Primary outcomes include perceived stress, role clarity, task mastery, and social acceptance. These outcomes will be measured during the first 13 weeks for the intervention group and at week 13 for the control group. All instruments use five-point Likert scales in Swedish, based on questionnaires previously validated in the Swedish context. Secondary outcomes include recovery, intentions to stay, and job satisfaction. These will be measured at months 4, 8, and 12 for the intervention group. The instruments use five- or seven-point Likert scales in Swedish, based on measures previously validated in the Swedish context.

Covariates

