Covariates will include variables related to the outcomes such as role clarity, task mastery, social acceptance and demographic factors, such as prior clinical experience before participation in the programme.

Definition of combined measures

Scale scores will be computed by summing items response format (0 - 4 or 0- 6 depending on the instrument).

Missing Data

The extent and pattern of missingness will be described. If indicated, sensitivity analyses may be performed.

Plan of statistical analyses

Statistical analyses will be conducted using SPSS Statistics, with support from experienced researchers and statisticians. All procedures and results will be verified for accuracy. The data will be checked for deviations from normality. The plan is to analyse and report data with descriptive statistics, ANOVA, and χ^2 . This to compare the mean scores of the study variables, including CI and p-values, to determine differences between control and intervention groups. A two-sided significance level of $p = .01$ will be applied. Bonferroni correction to control the family-wise error rate (FWER) will be used, adjusting the conventional threshold of $p = .05$ by dividing it by the number of tests. The effect size of mean differences could be included. To further examine differences between the control and intervention groups, linear regression analysis will be conducted. The models will include covariates. Consort guidelines will be used to support the analysis process.

6. Utilization, Dissemination, and Communication Plan

The interventions are expected to contribute to a sustainable working life for nurses by strengthening competence, reducing stress, and promoting retention. Results will be utilized to inform healthcare policy and organizational practices aimed at improving nurse retention and well-being. Results will be disseminated regionally, nationally, and internationally

through peer-reviewed scientific articles, conference presentations and to stakeholders and health care professionals. The project will result in the production of a doctoral thesis, where findings from all study components will be synthesized. To ensure broader communication, key outcomes will also be shared via media and networks.

References

- Duchscher, J. (2012). *From surviving to thriving. Navigating the first year of professional nursing practice*. Nursing the future, the voice of the new graduates.

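### Section 5 plans an unadjusted ANOVA and a covariate-adjusted regression of the same non-randomised contrast and names neither as primary; one regression on pre-programme covariates should decide.

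*Combined protocol and SAP*

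**What the plan says.** Section 5, Study design and study population: "A quantitative intervention design with a non-randomised design with a two-arm structure is planned". Controls are the September 2022 intake; the intervention arm is the February and September 2023 intakes. Under Outcome measures, controls report the four primary outcomes (perceived stress, role clarity, task mastery, social acceptance) at week 13 only.

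Section 4, Research participants, gives the sizes. Intervention: "Two groups (January 2023 and June 2023), each with 40–50 participants". Control: one group "with approximately 40-50 participants". Section 5 gives other start months for the intervention groups, which does not affect the sizes.

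Section 5, Plan of statistical analyses, names two analyses of the group contrast:
- "The plan is to analyse and report data with descriptive statistics, ANOVA" and χ², to compare mean scores "to determine differences between control and intervention groups".
- "To further examine differences between the control and intervention groups, linear regression analysis will be conducted". For this analysis only: "The models will include covariates".

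The same section applies a two-sided level of .01 and a Bonferroni division of .05 by a number of tests that it does not give. The only assumption check is of normality. The Covariates paragraph lists role clarity, task mastery, social acceptance and demographic factors such as prior clinical experience. Table 1 in section 4 gives regression for research question 1 and ANOVA with χ² for the questionnaire parts of questions 2 and 4.

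**The concern.** The two analyses answer the same question and can disagree. The plan does not say which is reported as the result, so the choice stays open after the data are seen.

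The first-named analysis is also the weaker one for this design. Nothing balances a 2022 intake against two 2023 intakes, and the plan itself treats prior clinical experience as related to the outcomes. An unadjusted mean comparison passes any imbalance in it into the estimate. That can create an apparent effect or hide a real one, depending on the direction.

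A secondary matter is that a classical ANOVA pools the variance. With about one control to two intervention nurses, pooling gives the wrong standard error if the variances differ, and no check of variances is planned.

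**Working it through.** **Inputs from the documents.** Controls 40–50. Intervention 2 × (40–50) = 80–100. Midpoint 45 versus 90. Two-sided level .01, z = 2.576. The plan gives no power calculation, SD, effect size or covariate correlation, so it has no figure of its own to reproduce here. Everything marked assumed is mine.

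**1. Bias from imbalance in the unadjusted comparison.** Assumed: prior experience in 30% of one arm and 50% of the other, worth 0.4 SD.
- Bias = (0.50 − 0.30) × 0.4 = 0.08 SD.
- SE = √(1/45 + 1/90) = 0.1826 SD, so the bias is 0.08/0.1826 = 0.44 SE.
- Rejection with no true effect = P(Z > 2.576 − 0.44) + P(Z < −2.576 − 0.44) = .0163 + .0013 ≈ .018.
- At 40:80 and 50:100 the result is .017 and .018.

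A wider assumed range was simulated at 45:90 and .01, with one pre-programme covariate imbalanced by 0.3–0.5 SD and no true effect:

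| Correlation with outcome | Unadjusted rejects | Adjusted rejects |
|---|---|---|
| 0.3 | 2.0–3.8% | about 1% |
| 0.5 | 3.9–11.2% | about 1% |
| 0.7 | 7.6–24.4% | about 1% |

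**2. Unequal variances, if the ANOVA is classical.** Let r be the control SD divided by the intervention SD (assumed).
- Pooled variance = (44r² + 89)/133. SE used = √(pooled variance/30), since 1/45 + 1/90 = 1/30. True SE = √(r²/45 + 1/90).
- Real error = 2 × P(Z > 2.576 × SE used / true SE).

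| r | SE used | True SE | Real error at nominal .01 |
|---|---|---|---|
| 0.67 | 0.165 | 0.145 | .003 |
| 1.25 | 0.199 | 0.214 | .017 |
| 1.5 | 0.217 | 0.247 | .024 |
| 2 | 0.258 | 0.316 | .036 |

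Simulation at 40:80 and 50:100 agrees (0.4%, 1.6%, 2.4%, 3.6%); Welch stays at 0.9–1.1%. Ordinary regression does not cure this. With the control residual SD at 1.5 times the intervention SD, the adjusted model with conventional standard errors still rejects 2.3%.

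**3. Two p-values per outcome.** With the covariate balanced on average, claiming success if either test passes .01 gives 1.3–1.9% for covariate correlations of 0.3–0.7.

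**4. Which covariates are safe.** Suppose the programme acts only through one listed covariate, shifted by 0.3–0.8 SD and correlated 0.3–0.7 with the outcome (assumed). The total effect is then 0.3 × 0.3 = 0.09 to 0.8 × 0.7 = 0.56 SD. The unadjusted test rejects in 1.9–67% of runs; the model adjusted for that covariate rejects in about 1%. The programme's effect has been adjusted away.

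**The case against.** The adjusted model is already planned, and much of the criticism can be pushed further than the text allows. Four stronger readings are tempting.

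- *ANOVA is the main test.* A reader might infer this from the order and from regression being brought in to look further. The plan does not say so, and Table 1 points the other way by listing regression for question 1, which covers all four primary outcomes. Table 1 does not settle the matter either, because that question concerns development over the first quarter rather than the group contrast. What stands is that section 5 and Table 1 must be reconciled.
- *The ANOVA assumes equal variances.* The form is not stated. The classical form is the usual reading, but Welch is not excluded. Nothing in the documents predicts unequal variances: the programme is offered to all eligible nurses, with no targeting of weaker ones. This limb is conditional and secondary.
- *Testing twice doubles the family of tests.* The Bonferroni rule already divides by the number of tests, so counting both analyses would control the family-wise error. What is missing is the count. The two tests are also strongly correlated, which is why the either-test error is 1.3–1.9% and not 2%.
- *Making the regression primary is enough.* With the plan's own covariate list it is not, as step 4 shows.

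In the worked example and the variance table, every error rate stays below .05 per test. What survives is the missing primary analysis and the absence of adjustment in the first-named one.

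**Conclusion.** The concern holds in this limited form: two analyses of one non-randomised contrast, no designated primary, no rule for disagreement, and section 5 and Table 1 differ on the method. I have high confidence in that part, which rests on the text alone.

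The size rests on assumptions. For a moderate imbalance in prior experience, the nominal .01 becomes about .018, and it rises well beyond that if the covariate is strongly prognostic and badly imbalanced. The variance figures (about .003 to .036) apply only if the ANOVA is classical and the SDs differ as assumed. At .05/4 = .0125 instead of the stated .01, the example gives .021 and SD ratios of 1.25, 1.5 and 2 give .020, .028 and .042, so the conclusion does not depend on the level chosen. This should be changed; it does not invalidate the study.

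**What to change.** In section 5, Plan of statistical analyses:

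1. Make one linear regression per primary outcome the single primary between-group analysis: group plus pre-programme covariates, with HC3 standard errors. Take the estimate, CI and p-value from it.
2. Name the covariates: prior clinical experience and any other pre-programme demographics recorded in both arms. The documents do not list these, so the plan must.
3. Leave week-13 role clarity, task mastery and social acceptance out of this model. They are primary outcomes that the programme targets, and controls report them only at week 13. Any model that includes them is exploratory.
4. Report unadjusted means with Welch intervals as description, without a significance claim.
5. Count only the primary models in the Bonferroni divisor.
6. Align Table 1 with section 5.
7. Because the plan is marked as reviewed on 2026-02-18, after the surveys scheduled for 2022 and 2023, date the change and say whether outcome data had been examined.

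The cost is SAP wording and a few degrees of freedom; SPSS can fit the model. There may be a gain: for an assumed effect of 0.5 SD at .01, power with 40–50 controls rises from 50–62% unadjusted to 55–67% or 66–78% if the covariate correlates 0.3 or 0.5 with the outcome. Adjustment does not remove the calendar-year difference, or the difference in intake season (autumn-only controls against February and September intakes). Both should be stated as limitations.

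### Holm's step-down procedure would hold the same family-wise error rate as the planned Bonferroni correction and never reject less: a cheap improvement, not an error

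*Combined protocol and SAP*

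**What the plan says.** The multiplicity rule is in Section 5, Plan of statistical analyses: "Bonferroni correction to control the family-wise error rate (FWER) will be used". How the threshold is to be reached comes in the same sentence: "adjusting the conventional threshold of $p = .05$ by dividing it by the number of tests". The sentence before it fixes a level: "A two-sided significance level of $p = .01$ will be applied". The number of tests is not given, and no stepwise procedure appears anywhere in the document.

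Section 5, Outcome measures, sets out the candidates for the family: "Primary outcomes include perceived stress, role clarity, task mastery, and social acceptance". It adds three more: "Secondary outcomes include recovery, intentions to stay, and job satisfaction", with measurement times given for the intervention group only.

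Section 4, Research participants, gives the expected numbers. For ProDeveloP: "Two groups (January 2023 and June 2023), each with 40–50 participants". For the control group: "with approximately 40-50 participants". There is no power calculation. The same analysis section promises confidence intervals as well as p-values, and plans both ANOVA and covariate-adjusted linear regression for the group comparison.

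**The concern.** Bonferroni compares every p-value with the same strict threshold. Holm orders the p-values and relaxes the threshold after each rejection. For four tests the thresholds are .0125, .0167, .025 and .05. The first step is Bonferroni itself, so Holm cannot lose a rejection, and its error control needs no assumption about how the outcomes are correlated.

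The difference is largest when several effects are real at once and power is moderate. This programme targets all four primary outcomes, and the control group is 40 to 50 nurses. Some real differences could therefore be reported as non-significant when a procedure with the same family-wise guarantee would have declared them.

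**Working it through.** **The plan's own level.** .05/4 = .0125 for the four primary outcomes, .05/5 = .01, and .05/7 = .0071 for all seven outcomes. The stated .01 corresponds to five tests, which matches neither count. The family therefore has to be named before any procedure, Holm included, can be written down. The calculations below use the four primary outcomes.

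**Inputs from the documents.** Four primary outcomes; 40–50 controls; 2 × (40–50) = 80–100 intervention nurses; two-sided tests; family level .05. The midpoint is 45 against 90.

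**Assumed inputs.** A standardised difference d of 0.5 or 0.3; a common correlation of 0.5 between outcomes (0 to 0.7 in the sensitivity check); no dropout. The plan supports relatedness only in kind: "Covariates will include variables related to the outcomes such as role clarity, task mastery, social acceptance".

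**Bounds in closed form.** The z-statistic has mean d/√(1/45 + 1/90) = d/0.1826, which is 2.739 for d = 0.5 and 1.643 for d = 0.3. The two-sided critical values are 2.498 at .0125 and 1.960 at .05.
- d = 0.5: power is Φ(2.739 − 2.498) = 0.595 at .0125 and Φ(2.739 − 1.960) = 0.782 at .05.
- d = 0.3: power is Φ(1.643 − 2.498) = 0.196 at .0125 and Φ(1.643 − 1.960) = 0.376 at .05.

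Bonferroni sits at the lower figure. Holm must lie between the two, and how far it moves depends on how many other outcomes are rejected.

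**Simulation** of four correlated z-statistics (normal approximation, 45 against 90, correlation 0.5):

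| Assumed truth and measure | Bonferroni (.0125) | Holm |
|---|---|---|
| Per-outcome power, d = 0.5 on all four | 0.60 | 0.69 |
| Per real outcome, d = 0.5 on three | 0.60 | 0.65 |
| Per real outcome, d = 0.5 on two | 0.60 | 0.62 |
| Per real outcome, d = 0.5 on one | 0.60 | 0.60 |
| Per-outcome power, d = 0.3 on all four | 0.20 | 0.24 |
| All four shown, d = 0.5 on all four | 0.29 | 0.50 |
| At least one shown, d = 0.5 on all four | 0.87 | 0.87 |
| Any false positive, no real effect | 4.3% | 4.3% |
| False positive on the fourth outcome, d = 0.5 on the other three | 1.3% | 3.2% |

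**Sensitivity.**
- With d = 0.5 on all four, per-outcome power goes from 0.53 to 0.62 at 40 against 80, and from 0.65 to 0.74 at 50 against 100.
- Simulated two-sample t-tests at 45 against 90 give 58.2% to 67.4% per outcome and 27.4% to 48.4% for all four.
- Across correlations 0 to 0.7, the t-test gain per outcome is 8 to 11 points at d = 0.5 and 2 to 4 points at d = 0.3.

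**Intervals.** The interval that matches a .0125 test has level 1 − .0125 = 98.75%. Any outcome that Holm rejects and Bonferroni does not has p above .0125, so its 98.75% interval from the same analysis includes zero. With d = 0.5 on all four, at least one such outcome occurs in about 29% of simulated studies.

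**The case against.** The strongest reply is that nothing here is wrong. Bonferroni is a valid, familiar correction and it is already written into the plan. That stands: a reader might infer that the plan's error control is faulty, or that Bonferroni is unsuitable for correlated outcomes, and the documents support neither.

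A reader might also take the rise from 0.60 to 0.69 as the expected gain. It needs a difference of 0.5 SD on all four outcomes at once, and the plan states no effect size. With fewer or smaller effects the gain shrinks to a few points or nothing. Nor does Holm make a wholly negative result less likely, because its first step is Bonferroni.

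The extra power is not entirely free. Both procedures keep the family-wise rate at or below .05, but Bonferroni is stricter on a null outcome when the others are real (about 1.3% against 3.2%). Bonferroni tests and intervals also agree with each other, which matters in a plan that promises both.

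Timing is a fair objection too. The document carries an update date of 2026-02-18, while the group-comparison surveys were scheduled from November 2022 to December 2023. Moving to a less strict rule now could look data-driven. The documents do not say whether any comparison has been run, so they support a condition on the change but not a suspicion.

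What survives is that Holm, on the same family, never rejects less under the same guarantee. That holds whatever the effect size, SD or correlation.

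**Conclusion.** This is an optional efficiency gain at no cost in sample size. Its direction is certain for any fixed family of tests; its size is not. At 45 against 90 with correlation 0.5, the gain per outcome is about 9 points if d = 0.5 on all four outcomes, 5 if three are real, 2 if two are real, none if one is real, and about 4 if d = 0.3 on all four. The clearest benefit is in showing all four outcomes together, 0.29 against 0.50 at d = 0.5. These figures rest on assumed effects and correlation, on expected recruitment, and on no dropout.

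Two matters lie outside this point. The mismatch between .01 and the number of outcomes has to be settled whichever procedure is used, and its effect on power should not be credited to Holm. And no multiplicity procedure addresses the non-randomised comparison with an earlier cohort.

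**What to change.** In Section 5, Plan of statistical analyses, replace both the fixed .01 sentence and the Bonferroni sentence. Changing only the second would leave two conflicting levels in the plan. Suggested text:

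> The control-versus-intervention p-values for the four primary outcomes, all from the one analysis named as primary, are tested with Holm's step-down procedure at a family-wise two-sided level of .05, and Holm-adjusted p-values are reported; all other tests lie outside this family and are reported as exploratory.

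This requires the sponsor to name either the ANOVA or the covariate-adjusted regression as primary. Report mean differences with 98.75% intervals, and state in advance that an outcome declared significant only at a later Holm step will have a 98.75% interval that includes zero. If the sponsor wants a larger family of m tests, Holm starts at .05/m and the interval level becomes 1 − .05/m.

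Date the change and make it before any group comparison is seen. If comparisons have already been seen, keep Bonferroni as the pre-specified analysis, with its number of tests stated, and label Holm supplementary.

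The cost is a few sentences and sorting four p-values, with no further participants or data. The downsides to accept are the mismatch between test and interval and the higher false-positive chance on a null outcome when the others are real, still below 5%.
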